## **Objectives**

### **A. Specific Aims**

Preschool is a critical period during which children develop fundamental motor skills, build confidence in their movement, and start a physical activity trajectory that follows through adolescence and beyond. Unfortunately, few sustainable interventions have succeeded in increasing preschool children's physical activity, and subsequently children are developing obesity at alarming rates. A simple, low-cost strategy is the addition of colorful markings (i.e. hopscotch, foursquare, fun trails) to existing playgrounds or open spaces. These "painted playgrounds" have been shown to be effective to increase physical activity in older school-aged children but remain understudied in preschool children. The proposed project will implement and test the effectiveness of a scalable playground stenciling intervention to increase physical activity and fundamental motor skills and decrease sedentary behaviors among preschool aged children attending childcare centers.

The aim of this pilot project is:

**Aim 1:** To test the effectiveness of a promising (cost-effective, easily scalable) playground stenciling intervention to increase physical activity, improve fundamental motor skills, and decrease sedentary behaviors of preschool aged children attending childcare facilities.

The aim will be achieved through a pilot project that is grounded in rigorous and reproducible methodology, meaning the results can be generalized to other parts of the state and held as a model throughout the country. We expect that children who attend the childcare center that receives the stenciling will have greater increases in moderate to vigorous physical activity (MVPA) and fundamental motor skill competency, and larger decreases in sedentary behavior, compared to children who attend the control facility (who will receive the stencils after an approximate 6 to 8-week delay). The main outcome variable will be percentage of recess time spent in MVPA, measured objectively using a physical activity monitor (i.e. accelerometer). Additional outcome variables include fundamental motor skill competency, measured using the validated Test of Gross Motor Development (TGMD-3; Ulrich, 2016), and the percentage of recess spent being sedentary (accelerometry). Parents will provide demographics of all consented children, and height and weight will be collected before and after the intervention. We do not expect changes in weight status during this short time period but will include obesity as a covariate to control for differences in MVPA that may be due to weight.

This project will test the effectiveness of a promising (cost-effective, easily scalable) playground stenciling intervention in order to validate the need for dissemination to numerous childcare centers across Louisiana. Ultimately, this pilot may launch an innovative strategy that has the potential to disrupt negative trends in obesity and sedentary behavior among Louisiana preschoolers.

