## Recruitment Methods

All parents of children between the ages of 3-6 years at the 4 selected childcare centers will receive an informational handout/flyer and consent form to participate in study procedures. Informational materials about the study may also be distributed to parents via email, mail, fax, phone, or in-person through the school. Children for whom a completed consent form is returned by their parent or legal guardian will be eligible to participate. We aim to recruit up to 72 children (18 per center) between August 2018 and February 2019.

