### **Setting**

All childcare evaluations and study procedures involving children will be conducted in the East Baton Rouge community, at selected DOE licensed Class A or B childcare centers. Each childcare center will be required to provide written documentation to allow the conduct of study procedures at that site.

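### The Specific Aims claim statewide generalizability and a national model, but four selected centers in one community, analyzed without a center term, do not supply it

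*Combined protocol and SAP*

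**What the plan says.** Section A (Specific Aims) states: "The aim will be achieved through a pilot project that is grounded in rigorous and reproducible methodology". The same sentence then draws an inference from that, without qualification: "meaning the results can be generalized to other parts of the state and held as a model throughout the country". The next paragraph of that section gives the purpose as testing the intervention "in order to validate the need for dissemination to numerous childcare centers across Louisiana".

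The design facts are elsewhere:

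- Recruitment Methods refers to "All parents of children between the ages of 3-6 years at the 4 selected childcare centers" and adds "We aim to recruit up to 72 children (18 per center) between August 2018 and February 2019".
- Setting says that procedures involving children "will be conducted in the East Baton Rouge community, at selected DOE licensed Class A or B childcare centers".
- Section B (Background) describes an intervention group against a wait-list control and names Louisiana preschoolers as the population of interest.
- Primary Endpoints and Data Analysis Plan specifies a repeated measures ANCOVA on child outcomes, with t-tests and chi-square tests of change. The covariates are age, sex, BMI z-score and sociodemographic characteristics. Center is not among them, and clustering is not mentioned.

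The available text gives no sampling method for centers, no criteria for representativeness and no random assignment of centers. It does not state how many of the four centers are in each arm. The Specific Aims use the singular ("We expect that children who attend the childcare center that receives the stenciling will have greater increases in moderate to vigorous physical activity"), which does not settle the split.

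**The concern.** How far a result carries to other centers depends on how many centers were studied, how they were chosen and how widely they are spread. Careful measurement and a reproducible protocol bear on other qualities: internal validity, and whether someone else could repeat the study. The step from rigor to generalizability therefore does not follow.

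What is at stake is how the result will be read. The intervention is applied to a playground, so the center is the unit of intervention, yet the planned tests take the child as the unit. A small child-level p-value, next to text promising statewide generalization, would invite a rollout decision that the data cannot support. Centers in one community also carry no information on variation between communities or states, whatever model is fitted.

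**Working it through.** **1. The plan's own figure.** 4 centers × 18 children = 72, which matches the stated maximum. The documents give no alpha, power, effect size, SD, ICC or dropout rate, so there is no power calculation to reproduce.

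**2. Claim against design.** This step needs no assumed number.

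| Needed for the claim | In the available text |
|---|---|
| Centers from more than one community | East Baton Rouge only |
| A stated way of choosing centers that represent the state or nation | Centers are called selected; no method is described |
| An analysis that allows for variation between centers | Child-level ANCOVA and t-tests; no center term |

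None of the three is met.

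**3. Illustration of center-level precision.** Inputs from the documents: 4 centers and up to 18 children per center. Assumed inputs: 2 centers per arm, ICC 0.05 to 0.20, no baseline adjustment. SD is the between-child SD of the outcome analyzed.

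SE = sqrt[(ICC + (1 − ICC)/18) × (1/2 + 1/2)], and half-width = t(0.975, 2 df) × SE with t = 4.303.

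| ICC (assumed) | SE (SD) | 95% half-width (SD) |
|---|---|---|
| 0 | sqrt(0.0556) = 0.236 | 1.01 |
| 0.05 | sqrt(0.1028) = 0.32 | 1.38 |
| 0.10 | sqrt(0.1500) = 0.39 | 1.67 |
| 0.20 | sqrt(0.2444) = 0.49 | 2.13 |

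Treating all 72 children as independent gives sqrt(2/36) × t(0.975, 70 df) = 0.236 × 1.994 = 0.47 SD. The row at ICC 0 shows that 2 degrees of freedom alone more than double the half-width.

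**4. Sensitivity to the split.** A 3 v 1 split also leaves 2 df, but the last factor becomes 1/3 + 1 = 4/3. Each half-width is then multiplied by sqrt(4/3) = 1.155, so 1.38 becomes 1.59 and 2.13 becomes 2.46.

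**5. Sensitivity to baseline.** If the SD and ICC refer to single-occasion values and the analysis uses change, the SE scales by sqrt[2(1 − r)], where r is an assumed baseline to follow-up correlation of center means. At ICC 0.10 the half-width is 1.67 × 1.00 = 1.67 SD at r = 0.5, 1.67 × 0.775 = 1.29 SD at r = 0.7 and 1.67 × 0.632 = 1.05 SD at r = 0.8. Baseline information would also narrow the child-level 0.47 SD, so the adjusted figures should not be set against it.

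**The case against.** The strongest reply is that this is aims prose. No endpoint, eligibility rule, sample size or test depends on the sentence, the project is called a pilot, and the section closes in hedged language. That limits the weight of the point but does not remove it. The hedges qualify a different sentence, and the generalizability clause states how the results are to be used.

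A second reply is that the half-widths concern clustering and not external validity. This stands. Forty centers in the same community would give a narrow interval and still say nothing about other parts of the state. The figures also rest on an ICC and a split that the documents do not give. They are offered only to show how little four centers can say about centers in general.

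Two stronger readings are tempting, and the documents do not support either:

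- A reader might infer that the data cannot separate a stencil effect from center differences at all. Both groups are measured at baseline and follow-up and the endpoint is change, so stable differences between centers cancel. The remaining problem is narrower: centers may change differently for reasons other than the stencils.
- A reader might infer that the centers are known to be a convenience sample. The text says they were selected and does not say how. Parts of the document were not available for review, so the supportable statement is that no sampling method is described in the available text.

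**Conclusion.** The point holds as an overstated claim, joined to an analysis section that does nothing to limit it. The generalizability sentence and the dissemination purpose go beyond what four selected centers in one community can show. That finding rests on stated facts alone: the number of centers, the setting, and the absence of a center term.

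The size is illustrative. The center-level half-width is about 1.4 to 2.1 SD against 0.47 SD with children treated as independent, assuming a 2 v 2 split, ICC 0.05 to 0.20 and no baseline adjustment. With change scores at ICC 0.10 and an assumed r of up to 0.8 it remains above 1 SD. The correction is worth making because it changes what the trial may conclude, although it alters no endpoint or sample size.

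**What to change.** **Specific Aims.** Replace the generalizability sentence with one along these lines: *The project will provide pilot evidence on effectiveness from four selected childcare centers in East Baton Rouge; generalization to other centers or communities will need a larger, multi-community sample of centers.* In the dissemination sentence, change *validate* to *inform*. The effectiveness aim can stay. The new text should not add feasibility as an aim, because no feasibility outcome is defined. It should not add estimation of between-center variation either, because four centers cannot estimate it usefully.

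**Primary Endpoints and Data Analysis Plan.** State how many centers are in each arm. State that intervention effects on change will be reported with uncertainty that reflects the center as the unit of intervention, for example by comparing center mean changes on 2 df. State that child-level p-values will not be used to support claims beyond the participating centers.

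**Cost.** The first part is wording only and yields a less favourable stated claim. The second part changes the analysis and will give wider intervals. Neither needs more children, visits or measurements.

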## B. Background

The significance of this project stems from Louisiana's prevalence of preschool obesity which is 60% higher than the national average: 13.8% of preschoolers in the state are obese compared to 8.4% nationally. Physical activity during early childhood is known to reduce the risk of being overweight or obese and therefore protect against the development of comorbidities, such as heart disease, diabetes, etc. later in life. Furthermore, at this young age the development of fundamental motor skills is highly related to physical activity and is therefore an important correlate to obesity. Despite assumptions that young children are active throughout the day, studies indicate that almost half of preschool play time is spent in sedentary activities. Over 80% of children spend some time in childcare settings by the age of 3 years, making childcare facilities an important venue for the promotion of fundamental motor skills and physical activity. As playground stenciling has been shown to increase moderate to vigorous physical activity (MVPA) during recess among older children, it is necessary to determine whether it has the same benefit for preschool aged children. Therefore, we propose to use a scientifically rigorous design (intervention vs. wait-list control) to determine the effectiveness of playground stenciling in Louisiana preschool aged children, a population burdened with an urgent, established obesity epidemic.

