### **Primary Endpoints and Data Analysis Plan**

The primary endpoints include change in MVPA and sedentary time during recess measured by accelerometry. The secondary outcome includes change in fundamental motor skills.

Statistical analyses will be performed with the latest version of SAS. Means, standard deviations, and Pearson correlations will be calculated to describe the sample and examine differences between the intervention and control group. Differences in center characteristics (e.g. racial distribution of participants) will be tested using t-tests and chi-square tests. A repeated measures ANCOVA model will be used to test for effects of playground stenciling on each dependent continuous variable (minutes/recess MVPA, minutes/day MVPA in childcare center, minutes/recess Sedentary behavior, minutes/day Sedentary behavior in childcare center, minutes/day MVPA total, minutes/day screen-time total). T-tests and chi-square tests will be used to determine whether changes in outcome variables were different between the intervention and control childcare centers. Covariates will include age, sex, BMI z-score, and sociodemographic characteristics.

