### **Vulnerable Populations**

This study will involve young children as participants (3-6 year olds). As such, the children's parents/legal guardians will provide written informed consent. Furthermore, the childcare director will provide written permission for recess observations and the implementation of playground stencils.

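### The plan gives no rule, random or otherwise, for which of the four centers is stenciled first, so center-specific changes over 6 to 8 weeks could be read as a stencil effect

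*Combined protocol and SAP*

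**What the plan says.** The Background section describes the comparison in these words: "we propose to use a scientifically rigorous design (intervention vs. wait-list control". It gives the purpose as determining whether stenciling is effective in Louisiana preschoolers. Specific Aims adds that the results can be generalized across the state and used to support dissemination.

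The intervention is given to centers, not to individual children. Specific Aims expects that "children who attend the childcare center that receives the stenciling will have greater increases" compared with children at "the control facility (who will receive the stencils after an approximate 6 to 8-week delay". Recruitment Methods places the study "at the 4 selected childcare centers" and gives the size: "We aim to recruit up to 72 children (18 per center". The number of centers per arm is not stated, and Specific Aims uses the singular for both arms.

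Objectives, Recruitment Methods, Procedures, the analysis plan and Setting do not say how a center becomes intervention or control, who decides, or when. On directors, Vulnerable Populations says only that "the childcare director will provide written permission for recess observations and the implementation of playground stencils". Prior Approvals likewise asks for the director's written approval at each site.

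The Procedures table has activity, motor skills, height and weight measured at baseline and follow-up in both arms. The primary endpoints are changes. The analysis plan says "A repeated measures ANCOVA model will be used to test for effects of playground stenciling on each dependent continuous variable". Its covariates are age, sex, BMI z-score and sociodemographic characteristics. Center characteristics are to be tested for differences, but no center term or center-level covariate is specified.

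**The concern.** With only a few centers, whatever determines the order of stenciling is tied to the arm. If the order is chosen and the choice relates to how recess is about to change at a center, the comparison carries that difference as well as the stencils. Child and family covariates cannot remove it, because it belongs to the center.

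The wording raises the stakes. A pilot that reports what it did can live with undescribed or chosen assignment. A study that calls itself rigorous, claims to determine effectiveness and looks to statewide dissemination is making a causal claim, and the allocation rule is the step that would support it.

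**Working it through.** **Inputs from the documents.** Four centers and 18 children per center (Recruitment Methods). Change from baseline as the primary endpoint (analysis plan). 4 × 18 = 72 reproduces the planned enrolment. This is a recruitment product, not a power calculation: no alpha, power, effect size, SD, ICC or allocation ratio is given.

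**Assumptions.** Two centers per arm. ICC of the change score (not of the level at one visit) of 0.05, 0.10 or 0.20. Child-level SD of change set to 1.

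**Step 1: what baseline measurement removes.** A difference that is the same at baseline and follow-up, such as playground size or the mix of families, largely cancels in the change score. A difference that arises between the two visits does not cancel: a staff change, a new recess routine, or a different season or measurement week. Recruitment runs from August 2018 to February 2019, and nothing requires the two arms to be measured in the same weeks.

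**Step 2: the chance center component.** Each center's own deviation in change has variance ICC. The mean of two centers has variance ICC/2, and the difference of two such means has ICC/2 + ICC/2 = ICC. Its SD is therefore √ICC. For comparison, the SD from sampling 36 children per arm within centers is √((1 − ICC) × 2/36).

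| ICC of change (assumed) | SD from centers, √ICC | SD from children within centers |
|---|---|---|
| 0.05 | 0.22 | √(0.95/18) = 0.23 |
| 0.10 | 0.32 | √(0.90/18) = 0.22 |
| 0.20 | 0.45 | √(0.80/18) = 0.21 |

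The center part equals the child part at ICC 0.05 and is about twice as large at 0.20. Enrolling more children in the same centers does not shrink it. A 1 v 3 split would be worse: √(ICC × (1 + 1/3)) = 0.26, 0.37 and 0.52.

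**Step 3: how this would look in a child-level test.** Simulating 20,000 data sets per ICC with no true effect, a t-test on children at nominal 0.05 rejects in about 15%, 25% and 38% of runs at ICC 0.05, 0.10 and 0.20. At ICC 0 it rejects in about 5%.

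**Step 4: what drawing lots would achieve.** Steps 2 and 3 describe chance clustering, which is the same size with or without lots. Lots would make the center component vary around zero rather than lean in a chosen direction. Two pairs with one draw each give 2 × 2 = 4 allocations, so the smallest randomization p is 1/4 = 0.25 one-sided and 2/4 = 0.50 two-sided. Unrestricted 2:2 allocation gives 6 allocations and 2/6 = 0.33 two-sided. Neither can reach 0.05.

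**The case against.** The strongest reply is that the plan is silent, not wrong. It never claims randomization, calls itself a pilot, and measures both arms before and after. Much of this stands. A reader might infer that the centers were not randomized, but the documents do not say so. They only fail to describe a method.

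A reader might also infer that directors decide who is stenciled first. The text does not support this. Directors give permission, and because control centers also receive stencils later, permission does not separate the arms.

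It is also fair that stable features of a center are largely dealt with by analyzing change, and that sociodemographic covariates and descriptive tests of center characteristics are planned. This narrows the risk to center-specific change over the study weeks, but nothing in the analysis plan addresses that part.

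Finally, lots among four centers leave considerable imbalance in the single draw that is made. And the draw may come too late: Procedures includes a survey about the COVID-19 stay-at-home order, while the Study Timeline ends the project on July 1, 2019, so this version appears to postdate the planned fieldwork. That is why the fix needs a reporting alternative as well as a draw.

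**Conclusion.** The point holds as an undescribed allocation under causal wording. No rule is given for which center is stenciled first, change from baseline protects only against stable differences, and no center-level adjustment is planned.

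The size of any selection bias cannot be estimated from the documents. The figures of 0.22, 0.32 and 0.45 SD measure chance center imbalance and should not be read as that bias. They rest on an assumed 2 v 2 split and on assumed ICCs of the change score. If the singular wording in Specific Aims meant one center per arm, center and arm could not be separated at all.

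Drawing lots would remove systematic selection in expectation, but it would not make four centers enough for a confirmatory claim. Conclusions should stay at pilot level either way.

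**What to change.** **If assignment is still open.** State the number of centers per arm. Once all four centers have agreed and baseline testing is done, form two pairs on playground and enrolment, measure both centers of a pair in the same calendar weeks, and draw lots within each pair for which is stenciled first. Record who makes the draw and when. Drawing after baseline also keeps consent and baseline testing free of knowledge of the arm.

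**If assignment was already made without randomization.** Say how it was made, describe the study as a non-randomized controlled pilot, and cut back the rigor, effectiveness and generalizability wording in Specific Aims and Background. Describing a chosen assignment makes the report honest but does not remove any bias.

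**In either case.** Report results by center, and state that chance imbalance between four centers limits what can be concluded.

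**Cost.** One paragraph and two draws. The lottery denies no center the stencils, since all receive them eventually. The real price is less freedom in scheduling: some centers wait for their partner, and the gap between baseline testing and stenciling may lengthen for those recruited early. The relabelling route costs only text edits.
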